11.1.1 Overview of AEs		
Population	:	Safety population
Contents	:	Overview AE table will be tabulated and will present number and percentages of subjects and number of events with following items. 
 • AEs • ADRs • AEs with fatal outcome • SAEs • AEs leading to premature discontinuation from the study • Events of special interest

11.1.2 Summary Table of AEs ADRs		
11.1.3 Summary Table of ADRs		
Population	:	Safety population
Contents	:	The number and percentage of incidences of AEs and ADRs in separate table by SOC and PT

11.1.3 Summary Table of AEs by Causality		
--	--	--

Population	:	Safety population
Contents	:	The number and percentage of incidences of AEs by causality based on SOC and PT

11.1.4 Summary Table of AEs by Severity

11.1.5 Summary Table of ADRs by Severity

Population	:	Safety population
Contents	:	The number and percentage of incidences of AEs, and ADRs by severity based on SOC and PT will be summarized.

Following Listings regarding AEs will be provided.

- AEs
- SAEs
- Subjects with deaths
- AEs leading to premature discontinuation from the study
- AEs with Non-Serious COPD Exacerbation

11.2 Laboratory Tests

11.2.1 Summary Table of Laboratory Test

Population	:	Safety population
Contents	:	Summary statistics for original value and change from Baseline will be provided The analysis variables are defined in appendix for laboratory parameter. For Laboratory results, a data listing will be provided.
Analysis Visit for 1401	:	Baseline, Week 5 , Week 9
Analysis Visit for 1401- OLE	:	Baseline, Ext Week 26, Ext Week 52

11.2.2 Summary Shift Table of Laboratory Test (Low, Normal and High)

11.2.3 Summary Shift Table of Laboratory Test (Normal and Abnormal)

Population	:	Safety population
Contents	:	Shift tables for laboratory test with normal range will be provided. The analysis variables are defined in appendix for laboratory parameter..
Analysis Visit for	:	Baseline, Week 5 , Week 9

1401		
Analysis Visit for 1401- OLE	:	Baseline, Ext Week 26, Ext Week 52

11.3 Vital Signs

11.3.1 Summary Table of Vital Signs		
Population	:	Safety population
Contents	:	Summary statistics for original value and change from Baseline will be provided. The analysis variables are displayed in Table C. For vital signs results, a data listing will be provided.
Analysis Visit for 1401	:	Week 1 prior to Infusion (Baseline) and Week 1 (After completion of infusion), Week 2 ~ Week 8 (Prior to infusion / After completion of infusion)
Analysis Visit for 1401- OLE	:	Week 1 prior to Infusion (Baseline), Ext Week 1 ~ Ext Week 52 (Prior to infusion / After completion of infusion)

Table C:

Contents	Digits to be displayed
Pulse rate [BEATS/MIN]	Integer
Systolic blood pressure [mmHg] Diastolic blood pressure [mmHg]	Integer
Body temperature [C]	1 decimal place
Respiratory rate [breaths per minute]	Integer

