At the screening visit (scheduled within 3 weeks before trial entry), after providing informed consent (agreement based on adequate explanation and understanding of the treatment plan), subjects will be evaluated for eligibility for participation during the screening period (refer to Section 4.2.1 “Inclusion Criteria” and Section 4.2.2 “Exclusion Criteria”). Subjects considered eligible will enter the 8-week treatment period to receive a total of 8 weekly intravenous infusions of 60 mg/kg of Alpha-1 MP. The initial intravenous infusion will be given at the Week 1 (baseline) visit. During the treatment period, subjects will receive weekly intravenous infusions of Alpha-1 MP at the Weeks 1 (baseline), 2, 3, 4, 5, 6, 7, and 8 visits. After the last intravenous infusion of Alpha-1 MP at the Week 8 visit, subjects will enter the 1-week PK evaluation period. During this PK evaluation period, subjects will visit the study center to undergo blood sampling for PK evaluation at the PK1 visit (the next day of the Week 8 visit), the PK2 visit (2 days after the Week 8 visit), the PK5 visit (5 days after the Week 8 visit), and at the Week 9 visit. At 30 days after the last dose (Week 8), subjects will visit the study center for follow-up/study completion (Week 12). All subjects will undergo blood sampling for the measurement of alpha₁-PI trough concentrations at the Weeks 1 (baseline), 7, and 8 visits (blood samples will be collected before dosing) as well as at the Week 9 visit.

Blood samples for the evaluation of PK parameters will be collected from Week 8 to Week 9. The blood sample collected before the infusion of Alpha-1 MP at the Week 8 visit and the blood sample for PK evaluation collected at the Week 9 visit (7 days after the infusion at the Week 8 visit) will be also used for the measurement of alpha₁-PI trough concentrations for Weeks 8 and

9. For details of the total of 10 sequential PK blood sampling time points, refer to Section 4.7.2.2 and Appendix 1.

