- c: Subjects not entering the extension trial (GTI1401-OLE) and subjects who receive Alpha-1 MP at any dose and discontinue this clinical trial early will be asked to return to the study center for the follow-up/study completion procedures and evaluations scheduled at the Week 12 visit. This visit should be made at the timing as close as possible to 4 weeks (i.e., 30 days) after the last dose of the investigational drug in the subject.
- d: CT densitometry scan should be performed anytime from the Screening Visit to the Week 1 (Baseline) Visit; if the CT densitometry scan is performed at the Week 1 (Baseline) Visit, then it must be performed prior to the first Alpha-1 MP infusion. This CT scan will measure lung density.
- e: Body weight will be used to calculate the Alpha-1 MP dose, and this recorded body weight will be used for dose calculation until the next scheduled body weight measurement.
- f: Blood samples for viral safety assessment (viral NAT and viral serologic test) will be collected before the intravenous infusions of Alpha-1 MP at the Week 1 (baseline) visit. However, the collected samples will be tested only if the subject shows clinical signs or symptoms suggestive of viral infection during the trial period. Only in this case will additional blood samples for viral NAT and viral serologic test be collected. All these collected blood samples will be stored until completion of all the tests in this clinical trial (GTI1401) and the extension trial (GTI1401-OLE).
- g: Sampling will be performed before each intravenous infusion of Alpha-1 MP.
- h: Vital signs will be checked immediately before and after each intravenous infusion of Alpha-1 MP.
- i: Pulmonary function tests after administration of a bronchodilator will be performed 15 to 30 minutes after administration of a bronchodilator. For a short-acting bronchodilator, subjects will receive 4 puffs of salbutamol given by an MDI and spacer in each pulmonary function testing. The same bronchodilator as that used at the start of the trial should be used throughout the trial period.
- j: Sampling will be performed in subjects with no previously documented alpha1-PI levels as measured by nephelometry (if it is unknown whether the subject's alpha1-PI level is <50 mg/dL or not).

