5.3 Safety Data Handling

5.3.1 Definition of Baseline

Baseline evaluations will be those collected (non-missing) closest to and prior to the first study drug infusion, which will be conducted –within 21 days of Week 1. For both GTI1401 and GTI1401-OLE, the baseline is the baseline visit at Week 1 in GTI1401 study.

For Pulmonary Function Tests

Values collected at “PRE-BRONCHODILATOR” time-point in screening visit will be defined as baseline for “PRE-BRONCHODILATOR”. Also values collected at “POST-BRONCHODILATOR” time-point in screening visit will be defined as baseline for “POST-BRONCHODILATOR”.

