 11.3 Vital Signs
 11.3.1 Summary Table of Vital Signs

Safety population

Pulse rate [BEATS/MIN]

Parameter	Original Value	Change from Baseline
Visit		
Statistics	Original Value	Change from Baseline
Week 1 IMMEDIATELY PRIOR TO START OF INFUSION (Baseline)		
N	xx x	-
Mean(S.D.)	xx x (xx x.)	-
Median	xx x	-
Min , Max	xx x , xx.x	-
Week 1 IMMEDIATELY AFTER COMPLETION OF INFUSION		
N	xx x	xx x
Mean(S.D.)	xx x (xx x.)	xx x (xx x.)
Median	xx x	xx x
Min , Max	xx x , xx.x	xx x , xx x
Week 2 IMMEDIATELY PRIOR TO START OF INFUSION		
N	xx x	xx x
Mean(S.D.)	xx x (xx x.)	xx x (xx x.)
Median	xx x	xx x
Min , Max	xx x , xx.x	xx x , xx x
Week 2 IMMEDIATELY AFTER COMPLETION OF INFUSION		
N	xx x	xx x
Mean(S.D.)		xx x (xx x.)
Median	xx x	xx x
Min , Max	xx x , xx.x	xx x , xx x
. . .		
Week 9 IMMEDIATELY AFTER COMPLETION OF INFUSION		
N	xx x	xx x
Mean(S.D.)	xx x (xx x.)	xx x (xx x.)
Median	xx x	xx x
Min , Max	xx x , xx.x	xx x , xx x

GTI 1401
11 Safety Analysis

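### After Week 1, no same-visit post-minus-pre change in vital signs is summarised or listed, although both readings are taken at every infusion

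*SAP*

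**What the plan says.** **Collection.** Protocol Appendix 1, note h: "Vital signs will be checked immediately before and after each intravenous infusion of Alpha-1 MP". Protocol 4.1.1 plans "a total of 8 weekly intravenous infusions of 60 mg/kg of Alpha-1 MP", so each subject can contribute 8 before-and-after pairs per vital sign.

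**Analysis.** SAP 11.3.1 plans two quantities at each time point: "Summary statistics for original value and change from Baseline will be provided". The GTI1401 time points are "Week 1 prior to Infusion (Baseline) and Week 1 (After completion of infusion" and then "Week 2 ~ Week 8 (Prior to infusion / After completion of infusion". For the extension, SAP 11.3.1 sets the pre- and post-infusion readings of Ext Weeks 1 to 52 against the same GTI1401 Week 1 pre-infusion value.

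**Baseline.** SAP 5.3.1 fixes it once: "For both GTI1401 and GTI1401-OLE, the baseline is the baseline visit at Week 1 in GTI1401 study".

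**Output shells.** Layout Plan Table 11.3.1 has one column for the original value and one for change from Baseline. The row "Week 1 IMMEDIATELY AFTER COMPLETION OF INFUSION" has an entry in both. Listing 11.3.2 shows each subject's values by parameter and visit, with change from baseline. Neither shell has a column for change within a visit.

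**The concern.** Reading vital signs on both sides of an infusion allows each subject to serve as his or her own control over a short interval. The natural summary is post minus pre at the same visit. The only change score planned uses a fixed reference that is up to 7 weeks old by Week 8. In the extension the reference is up to 59 weeks old: Week 9 is Ext Week 1, which is 8 weeks after Week 1, and Ext Week 52 is 51 weeks after that.

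The primary objective (Protocol 3.1) is the safety of weekly infusions. Protocol 5.1 warns of anaphylactic reactions, and Protocol 1.3 lists chills and hot flush among suspected drug reactions in an earlier study. A summary of the immediate response to each infusion bears directly on that objective. The spread and extremes matter most, because with about 3 subjects the useful question is whether any one of them had a large acute change.

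**Working it through.** The documents state no figure on this point (no power, effect size or SD for vital signs), so there is none to reproduce. The check has four steps.

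**1. What the change column contains.** Write pre_k and post_k for the readings at Week k, and base = pre_1.

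- Week 1: post_1 − base = post_1 − pre_1, the acute change.
- Weeks 2 to 8: post_k − base = (post_k − pre_k) + (pre_k − pre_1), the acute change plus drift since Week 1.

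The acute change is summarised directly for 1 of 8 infusions in GTI1401, and for 0 of 52 scheduled weeks in the extension. At the minimum of 3 subjects there are 3 × 8 = 24 pairs per vital sign, of which 3 × 1 = 3 are summarised as pairs.

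**2. Recovering the mean.** With complete data, mean(post_k − base) − mean(pre_k − base) = mean(post_k − pre_k). Made-up data for three subjects:

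| Subject | base | pre_k | post_k | pre_k − base | post_k − base | post_k − pre_k |
|---|---|---|---|---|---|---|
| 1 | 70 | 74 | 86 | 4 | 16 | 12 |
| 2 | 80 | 78 | 88 | −2 | 8 | 10 |
| 3 | 90 | 95 | 103 | 5 | 13 | 8 |
| Mean | | | | 2.33 | 12.33 | 10.0 |

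Row subtraction gives 12.33 − 2.33 = 10.0, which is the paired mean. If subject 3's post value is missing, it gives (16 + 8)/2 − 2.33 = 9.7, while the paired mean of the two complete subjects is (12 + 10)/2 = 11.0. SAP 5.2 and 5.3.2 leave missing values missing, so the two rows can then describe different subjects.

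**3. Recovering the spread.** Keep the same pre and post values but set all three baselines to 80. The change columns now carry no information on which pre value belongs with which post value.

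- Pairing as in the table: changes 12, 10, 8; mean 10.0, median 10, SD 2.0.
- Pre values reassigned as 95, 74, 78: changes −9, 14, 25; mean 10.0, median 14, SD 17.3.

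Every planned row of Table 11.3.1 is identical in the two cases. The table therefore does not in general determine the SD, median, minimum or maximum of the acute change. With exactly 3 subjects and differing baselines, a patient reader might deduce the pairing, because minimum, median and maximum are then the three values themselves. That would be a reconstruction, not a planned summary.

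**4. Precision, under assumptions.** With equal variances s², SD(post_k − base) = s√(2(1 − ρ_between)) and SD(post_k − pre_k) = s√(2(1 − ρ_within)). The ratio is √((1 − ρ_between)/(1 − ρ_within)). The correlations are assumed; the documents give none.

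| ρ_between | ρ_within 0.7 | 0.8 | 0.9 |
|---|---|---|---|
| 0.3 | 1.53 | 1.87 | 2.65 |
| 0.5 | 1.29 | 1.58 | 2.24 |
| 0.7 | 1.00 | 1.22 | 1.73 |

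The SD of change from Week 1 is thus about 1.0 to 2.6 times that of the same-visit change. The lower end is no difference.

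**The case against.** A reader might infer that the acute effect of infusion is never estimated, or that vital signs are analysed only as change. The documents do not support either. At Week 1 the post-infusion change from Baseline is the paired acute change, with N, mean, SD, median, minimum and maximum in the shell. Original values are also summarised before and after infusion at each of Weeks 1 to 8.

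A reader might also infer that drift hides the acute effect and that its noise dominates with 3 subjects. The pre and post rows of a visit share one baseline, so with complete data drift cancels when they are subtracted. The claim that noise dominates would rest on correlations that nobody has supplied.

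Three further arguments carry weight. Listing 11.3.2 shows every subject's values, so at the minimum sample size each of the 24 pairs per parameter needs one subtraction. A fixed study baseline is the SAP's stated rule and is applied consistently, so this is not a contradiction. Acute reactions also have other routes to detection: the adverse-event evaluation in the protocol synopsis covers abnormal vital-sign changes, subjects are observed for at least 30 minutes after each infusion, and infusion interruptions are tabulated by visit (SAP 9.2.2).

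All of this limits the size of the point without removing it. Hand subtraction over 5 parameters, 8 infusions and 3 subjects is 5 × 8 × 3 = 120 calculations before the extension is counted, and it is not a planned analysis. Adverse-event reporting depends on someone judging a change to be unfavourable, whereas a table summarises all of them.

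**Conclusion.** The point holds in a limited form. For infusions 2 to 8, and for all extension infusions, no same-visit change in vital signs is summarised or listed, and the change that is shown mixes acute response with drift since Week 1. The paired mean is recoverable if data are complete; the paired SD, median and range in general are not recoverable from the table.

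The impact is modest. The analysis is descriptive, with no test or sample-size calculation affected, and no data are lost because individual values are listed. The count of 1 of 8 (and 0 of 52 in the extension) follows from the documents alone. The 1.0 to 2.6 range for the SD ratio rests on equal variances and on assumed correlations of 0.3 to 0.7 between visits and 0.7 to 0.9 within a visit, so no particular gain in precision should be claimed.

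**What to change.** In SAP 11.3.1, define a within-visit change: the post-infusion value minus the pre-infusion value of the same visit, calculated only where both are present. Add it to Table 11.3.1 (N, mean, SD, median, minimum, maximum) and to Listing 11.3.2 for each of Weeks 1 to 8, and likewise for the GTI1401-OLE infusion visits. Keep change from the Week 1 baseline for the pre-infusion values, where it properly describes drift over the study.

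The cost is one derived variable and one column in each output. No new measurement, visit or subject is needed. Directly summarised infusions go from 1 of 8 to 8 of 8 in GTI1401, and from 0 of 52 to 52 of 52 scheduled weeks in the extension.

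While the shell is open, one separate item needs reconciling: it carries a Week 9 post-infusion row, whereas SAP 11.3.1 stops at Week 8 for GTI1401 and that study has no Week 9 infusion.

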11.4 Electrocardiogram

11.4.1 Summary Table of Electrocardiogram		
Population	:	Safety population
Contents	:	Shift tables for electrocardiogram will be provided. The analysis variables are displayed in Table D. For electrocardiogram results, a data listing will be provided.
Analysis Visit for 1401	:	Baseline, Week 9
Analysis Visit for 1401-OLE	:	Baseline, Ext Week 26, Ext Week 52

Table D:

Contents	Category
Electrocardiogram	Normal Abnormal

11.5 Urine Cotinine Test

11.5.1 Summary Table of Urine Cotinine Tests		
Population	:	Safety population
Contents	:	Shift table will be provided for Baseline value and the change from Baseline. The analysis variables are displayed in Table E.
Analysis Visit for 1401	:	Baseline, Week 5, Week 9
Analysis Visit for 1401-OLE	:	Baseline, Ext Week 26, Ext Week 52

Table E:

Contents	Category
Urine cotinine result	Negative Positive

11.6 Pulmonary Function Tests

11.6.1 Summary Table of Pulmonary Function Tests (FEV ₁ and FVC)		
Population	:	Safety population
Contents	:	Summary statistics for original value and change from Baseline value will be provided for both “PRE-BRONCHODILATOR” and “POST-BRONCHODILATOR” separately. The analysis variables are displayed in Table F.
Analysis Visit for 1401	:	Screening, (Baseline), Week 5, Week 9
Analysis Visit for 1401-OLE	:	Screening (Baseline), Ext Week 26, Ext Week 52

11.6.2 Summary Table of Pulmonary Function Tests (FEV ₁ % Predicted)		
Population	:	Safety population
Contents	:	Frequency counts and summary statistics will be provided for both “PRE-BRONCHODILATOR” and “POST-BRONCHODILATOR” separately. The analysis variables are displayed in Table F.
Analysis Visit for 1401	:	Screening, (Baseline), Week 5, Week 9
Analysis Visit for 1401-OLE	:	Screening (Baseline), Ext Week 26, Ext Week 52

Table F:

Contents	Digits to be displayed
Best FEV ₁ [L]	2 decimal place
Best FVC [L]	2 decimal place
FEV ₁ predicted [%]	Integer
FEV ₁ predicted [%] category	0= \leq < 30 30= \leq < 70 70= \leq < 100

For Pulmonary Function Tests, a data listing will be provided.

11.7 Pregnancy Tests

For pregnancy test, a data listing will be provided.

11.8 CT Scan

For CT Scan (densitometry), a data listing including lung density will be provided.

11.9 Physical Examination

For physical examination, a data listing will be provided.

12 Interim Analysis

No interim analysis is planned.

13 Changes in Planned Analysis

There are no changes in the planned analysis.

Appendix 1 Schedule of Study Procedures – GTI1401

Trial period	Screening	Treatment ^a												Follow-up
	Day -21 to the day before Week1	Week 1 (baseline)	Week 2	Week3	Week 4	Week 5	Week 6	Week 7	Week 8	PK1	PK2	PK5	Week 9 (Study completion) ^b	Week 12 (Study completion) ^c
Informed consent	X													
Inclusion/exclusion criteria	X	X												
Assignment of subject number	X													
Medical history	X													
Age, sex	X													
CT Scan (densitometry)	X ^d													
Physical examination (excluding breast and urogenital examination)	X												X	X
Body height	X													
Body weight	X	X ^e				X ^e								
Blood sampling for viral safety assessment ^f		X												
Urine pregnancy test (Only in women of childbearing potential)	X					X							X	X
Urinary cotinine level	X					X							X	X
Blood and urine sampling for laboratory tests (Hematology, blood chemistry, urinalysis)	X	X ^g				X ^g							X	X
Vital signs (Pulse rate, blood pressure, respiratory rate, body temperature) ^h		X	X	X	X	X	X	X	X				X	X
12-lead ECG	X	X											(X)	
Pulmonary function tests before and after administration of a bronchodilator (FEV ₁ and FVC) ⁱ	X ⁱ					X ⁱ							X ⁱ	X ⁱ
Blood sampling for alpha ₁ -PI concentration measurement	X ^j	X ^g						X ^g	X ^k	X ^k	X ^k	X ^k	X ^k	
Intravenous infusion of Alpha-1 MP ^l		X	X	X	X	X	X	X	X					
Observation of subjects after infusion of Alpha-1 MP ^m		X	X	X	X	X	X	X	X					
Evaluation of COPD exacerbations	X	X	X	X	X	X	X	X	X	X	X	X	X	X
Evaluation of adverse events	X	X	X	X	X	X	X	X	X	X	X	X	X	X
Evaluation of concomitant medications	X	X	X	X	X	X	X	X	X	X	X	X	X	X

- a: The date of individual visits will be determined in relation to the date of the Week 1 (baseline) visit. The date of all visits after the screening visit and the Week 1 (baseline) visit will be arranged within a time window of ± 1 day. The PK evaluation period will start at the Week 8 visit and end at the Week 9 visit.
- b: At the Week 9 visit, subjects will be asked whether or not they would like to enter the extension trial (GTI1401-OLE). For subjects eligible for participation in the extension trial, the Week 9 visit will be the study completion visit for this clinical trial (GTI1401).
- c: Subjects not entering the extension trial (GTI1401-OLE) and subjects who receive Alpha-1 MP at any dose and discontinue this clinical trial early will be asked to return to the study center for the follow-up/study completion procedures and evaluations scheduled at the Week 12 visit. This visit should be made at the timing as close as possible to 4 weeks (i.e., 30 days) after the last dose of the investigational drug in the subject.
- d: CT densitometry scan should be performed anytime from the Screening Visit to the Week 1 (Baseline) Visit; if the CT densitometry scan is performed at the Week 1 (Baseline) Visit, then it must be performed prior to the first Alpha-1 MP infusion. This CT scan will measure lung density.
- e: Body weight will be used to calculate the Alpha-1 MP dose, and this recorded body weight will be used for dose calculation until the next scheduled body weight measurement.
- f: Blood samples for viral safety assessment (viral NAT and viral serologic test) will be collected before the intravenous infusions of Alpha-1 MP at the Week 1 (baseline) visit. However, the collected samples will be tested only if the subject shows clinical signs or symptoms suggestive of viral infection during the trial period. Only in this case will additional blood samples for viral NAT and viral serologic test be collected. All these collected blood samples will be stored until completion of all the tests in this clinical trial (GTI1401) and the extension trial (GTI1401-OLE).
- g: Sampling will be performed before each intravenous infusion of Alpha-1 MP.
- h: Vital signs will be checked immediately before and after each intravenous infusion of Alpha-1 MP.
- i: Pulmonary function tests after administration of a bronchodilator will be performed 15 to 30 minutes after administration of a bronchodilator. For a short-acting bronchodilator, subjects will receive 4 puffs of salbutamol given by an MDI and spacer in each pulmonary function testing. The same bronchodilator as that used at the start of the trial should be used throughout the trial period.
- j: Sampling will be performed in subjects with no previously documented alpha1-PI levels as measured by nephelometry (if it is unknown whether the subject's alpha1-PI level is <50 mg/dL or not).

- k: Sampling time points of PK samples: 1) Immediately before the intravenous infusion; 2) Immediately after the intravenous infusion (after flushing the infusion line with physiological saline) (at 0 hours); 3) At 15 minutes after completion of the intravenous infusion; 4) At 2 hours after completion of the intravenous infusion; 5) At 4 hours after completion of the intravenous infusion; 6) At 8 hours after completion of the intravenous infusion; 7) At 24 ± 4 hours (1 day after completion of the intravenous infusion); 8) At 48 ± 4 hours (2 days after completion of the intravenous infusion); 9) At 120 hours \pm 1 day (5 days after completion of the intravenous infusion); and 10) At 168 hours \pm 1 day (7 days after completion of the intravenous infusion) (Week 9).
- l: Weekly intravenous infusions of 60 mg/kg of Alpha-1 MP will be given under the supervision of the investigator or a designated person at each study center.

